### Statistical Analysis

- Kaplan-Meier survival analysis for RFS and PFS.
- Chi-square tests for categorical variables.
- Cox proportional hazards model for multivariate analysis.
- P-value <0.05 considered statistically significant.

### Results Summary

- A total of 125 patients were analyzed: 61 in the BCG RIVM group and 64 in the BCG Russian group.
- No significant difference in RFS or PFS between the groups.
- Adverse event rates were comparable.

## **Conclusion**

This trial demonstrates that BCG RIVM and Russian substrains offer similar efficacy and safety for the treatment of NMIBC. These findings provide flexibility in substrain selection based on availability and institutional preference.

---

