## **Objectives**

- **Primary Objective:** To evaluate the efficacy of BCG RIVM versus BCG Russian substrains in terms of recurrence-free survival (RFS) and progression-free survival (PFS).
- **Secondary Objective:** To compare the safety and adverse event profiles between the two substrains.

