## **Exclusion Criteria**

1. Inadequate BCG therapy (fewer than 5 induction doses or fewer than 2 maintenance doses).
2. Follow-up period less than 12 months.
3. Use of multiple BCG strains.
4. Previous history of BCG therapy.

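### The conclusion claims demonstrated similarity, but the plan only tests for a difference at P<0.05 and sets no margin

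*Combined protocol and SAP*

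**What the plan says.** The Objectives section sets an ordinary comparison as the primary aim: "To evaluate the efficacy of BCG RIVM versus BCG Russian substrains in terms of recurrence-free survival (RFS) and progression-free survival (PFS". The secondary aim is a comparison of safety. Neither is framed as equivalence or non-inferiority.

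The Statistical Analysis section lists Kaplan-Meier analysis, "Chi-square tests for categorical variables" and "Cox proportional hazards model for multivariate analysis". Its only decision rule is "P-value <0.05 considered statistically significant", and it does not say whether that is one- or two-sided. No section gives a margin, a power statement or a criterion based on a confidence interval.

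The Results Summary reports "No significant difference in RFS or PFS between the groups" for 61 and 64 analysed patients, and describes adverse event rates only as comparable. It gives no event counts, hazard ratios, intervals, rates or P-values.

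The Conclusion then states: "This trial demonstrates that BCG RIVM and Russian substrains offer similar efficacy and safety for the treatment of NMIBC". Its second sentence derives freedom to choose between the substrains from that.

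**The concern.** A test against a null of no difference can reject that null or fail to reject it. Failing to reject it says the data are compatible with no difference. It does not say they are incompatible with a large one. To demonstrate similarity, the trial would have to rule out differences beyond some stated size, and no such size is defined. The gap applies equally to efficacy and safety, since a non-significant chi-square test is no better evidence of similarity than a non-significant survival comparison.

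This is the headline statement on both the primary and the secondary objective, and a practical inference about interchangeable use is built on it. The phrase 'no significant difference' covers results from near-identical arms to a possible doubling of the hazard. A reader of these documents cannot tell where the trial fell.

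**Working it through.** **Inputs.** Arm sizes are 61 and 64 (Randomization, Results Summary), and 61 + 64 = 125 agrees with the stated total. The threshold is 0.05 (Statistical Analysis); two-sided is assumed. There is no power or sample-size figure to reproduce. Event counts, adverse event rates and margins below are assumptions, used only to show size. The logical gap depends on none of them.

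**Step 1: hazard ratios that count as non-significant.** With *d* total events, split roughly as the patients are,

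SE(log HR) = √[125² / (61 × 64 × *d*)] = √(4.0023 / *d*).

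The non-significant range is exp(±1.96 × SE). An observed HR at the upper edge of that range has an upper 95% limit of exp(2 × 1.96 × SE).

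| Assumed events | SE | Non-significant observed HR | Power for a true HR of 2 |
|---|---|---|---|
| 25 (20%) | 0.400 | 0.46 to 2.19 | 41% |
| 62 (50%) | 0.254 | 0.61 to 1.65 | 78% |
| 125 (all) | 0.179 | 0.70 to 1.42 | 97% |

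The last row is a ceiling, because no endpoint can have more than 125 first events. Even there, the upper limit at the edge is exp(2 × 1.96 × 0.1789) = 2.02. If the rule were one-sided, the limit at 125 events would be exp(1.645 × 0.1789) = 1.34, or 0.75 in the other direction. RFS and PFS each have their own count, so each has its own row.

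**Step 2: what could have been shown with a margin.** Take 125 events, a true HR of 1 and a margin *M*. Non-inferiority power (one-sided 2.5%) is Φ(ln *M* / SE − 1.96). Equivalence power (two one-sided 5% tests) is 2Φ(ln *M* / SE − 1.645) − 1, or zero if that is negative.

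| *M* | ln *M* / SE | Non-inferiority | Equivalence |
|---|---|---|---|
| 1.3 | 1.466 | 31% | 0% |
| 1.5 | 2.266 | 62% | 47% |
| 1.65 | 2.799 | 80% | 75% |

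Equivalence power reaches 80% only at exp[(1.645 + 1.2816) × 0.1789] = 1.69. In one direction a tighter margin could still be met by a favourable result: the upper 95% limit falls below 1.3 if the observed HR is below exp(ln 1.3 − 1.96 × 0.1789) = 0.92, and below 1.5 if it is below 1.06. Two-directional similarity within 1.3 could not be shown at all, since 1.645 × 0.1789 = 0.294 exceeds ln 1.3 = 0.262.

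**Step 3: safety.** For assumed RIVM rates near 10%, 20% and 30%, the table shows the largest Russian count that stays non-significant by uncorrected chi-square, with a Wald 95% interval for the difference (Russian minus RIVM, percentage points).

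| RIVM | Russian | P | Difference (95% CI) |
|---|---|---|---|
| 6/61 (10%) | 14/64 (22%) | 0.066 | 12.0 (−0.5 to 24.6) |
| 12/61 (20%) | 22/64 (34%) | 0.065 | 14.7 (−0.6 to 30.0) |
| 18/61 (30%) | 29/64 (45%) | 0.068 | 15.8 (−0.9 to 32.5) |

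These are edge cases by construction. If instead both arms had the same rate, between 10% and 50%, the half-width 1.96 × √[p(1 − p)(1/61 + 1/64)] would still be 10.5 to 17.5 points.

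**The case against.** The strongest reply is that the Results Summary is three bullets long. Counts and intervals may exist elsewhere, and they may be narrow enough to support a modest claim of similarity. It is fair that their absence here does not show they were never computed. But no margin was set in advance against which to judge them, and the Conclusion rests on what is reported, which is non-significance.

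A second reply is that 'similar' is only descriptive. The verb used is a claim of demonstration, and the next sentence draws a practical consequence from it.

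A third is that the illustrations are hypothetical. The efficacy ceiling of 125 events is not a plausible count, and the safety examples are worst-edge values, always with the Russian arm higher. That is true, and they should be read as bounds. The ceiling favours the trial, however, and realistic counts widen the range. Non-inferiority figures also answer a one-directional question, whereas similarity is two-directional; the equivalence figures are less favourable still. Nor does the plan say whether a continuity correction applies or tie the chi-square test to adverse events. With the correction, 15/64, 23/64 and 30/64 would also be non-significant (P = 0.073, 0.068 and 0.070).

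Finally, the plan mentions Cox regression only for multivariate analysis, so an adjusted hazard ratio with its interval would also help close the gap. That stands: the choice of model is secondary to reporting an interval at all.

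**Conclusion.** The concern holds. The Conclusion does not follow from the stated objectives, decision rule and results, and no other section repairs it. This is true whatever the unreported event counts are.

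The size rests on assumed counts, a two-sided 5% rule and the usual approximation for the variance of a log hazard ratio. At best, non-significance leaves observed hazard ratios from 0.70 to 1.42 open, with an interval that can reach about 2.0. With events in half the patients the range is 0.61 to 1.65. Under the assumed adverse event rates, differences of 12 to 16 points would pass as non-significant, with upper limits of about 25 to 33 points. The trial may be reported as not having found a difference, but not as having demonstrated similarity. This must be corrected.

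**What to change.** 1. Replace the first sentence of the Conclusion with wording such as: *No statistically significant difference in RFS or PFS was detected. Adverse event rates are given by arm with the difference and its 95% confidence interval. These results do not establish that the substrains are similar in efficacy or safety.*
2. In the Results Summary, add events per arm and the RIVM:Russian hazard ratio with a two-sided 95% interval, separately for RFS and PFS. A Cox model with treatment arm as its only term is the simplest main estimate, with any multivariable model as support. Add adverse event rates per arm with the difference and 95% interval.
3. Say which differences are excluded, using those intervals only, and note that they describe the 125 analysed patients. The Exclusion Criteria remove patients for "Inadequate BCG therapy (fewer than 5 induction doses or fewer than 2 maintenance doses" and for "Follow-up period less than 12 months". Both are known only after treatment has started, and an interval does not capture any bias that results.
4. Remove the flexibility sentence as a finding of the trial. Any margin applied now is post hoc, must be labelled exploratory, and cannot restore the claim.

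The cost is rewording, an arm-only Cox fit for two endpoints, and rate differences from data already collected. The downside is a less favourable conclusion and slightly longer reporting.

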## **Study Design**

This is a randomized prospective clinical trial conducted at Ankara University Ibni Sina Hospital from January 2019 to December 2022.

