## **Inclusion Criteria**

1. Age  $\geq 18$  years.
2. Histopathologically confirmed NMIBC (Ta, T1, or CIS).
3. Intermediate-, high-, or very high-risk classification based on EAU guidelines.
4. No prior BCG therapy within the last year.
5. No evidence of upper urinary tract carcinoma or distant metastases.
6. Minimum follow-up period of 12 months.

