### Intervention

Both groups received an induction course of six weekly intravesical BCG instillations, followed by maintenance therapy as per risk stratification protocols.

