### Outcome Measures

- **Primary Outcomes:**
  - Recurrence-free survival (RFS): Time from randomization to tumor recurrence.
  - Progression-free survival (PFS): Time from randomization to disease progression.
- **Secondary Outcomes:**
  - Adverse events: Assessed using the National Cancer Institute Common Terminology Criteria for Adverse Events (CTCAE).

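### The Conclusion claims similar efficacy on RFS and PFS with no time horizon, event counts or intervals, resting only on non-significant differences over a follow-up that is not reported

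*Combined protocol and SAP*

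**What the plan says.** The Conclusion reads: "This trial demonstrates that BCG RIVM and Russian substrains offer similar efficacy and safety for the treatment of NMIBC". It attaches no time point, estimate or interval, and it does not separate recurrence from progression. PFS is not named there. It enters because the Objectives define the efficacy comparison through RFS and PFS jointly, and Outcome Measures lists both as primary without ranking them. PFS is defined as "Time from randomization to disease progression", with no horizon.

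On duration, the Inclusion Criteria require "Minimum follow-up period of 12 months" and the Exclusion Criteria remove patients with "Follow-up period less than 12 months". Study Design places the trial "from January 2019 to December 2022" and does not say whether that window is accrual alone or accrual plus follow-up.

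The Results Summary gives the group sizes (61 and 64) and reports that neither survival outcome differed significantly. No median follow-up, number of events, number at risk, hazard ratio or confidence interval appears in any section.

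**The concern.** A Kaplan-Meier or Cox comparison supports statements only over the period observed, and only as precisely as the number of events allows. The Conclusion goes from a non-significant test to a demonstration of similarity and states neither the period nor the precision. For PFS, the documents let a reader rely on 12 months of observation per patient and nothing more.

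The Conclusion also goes on to support choosing a substrain by availability and institutional preference. A reader acting on that would take progression as settled, although the documents report nothing from which the size of a remaining difference could be judged.

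This overlaps with the absence of an equivalence margin but is not the same point. A margin would not supply a time horizon, and a horizon would not supply a margin.

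**Working it through.** The documents contain no sample-size calculation, power, event target or effect size, so there is no design figure to reproduce. Two sums can be checked and both are right: 61 + 64 = 125 patients, and January 2019 to December 2022 is 4 × 12 = 48 months.

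**Inputs from the documents**
- N = 125, with arm shares 61/125 = 0.488 and 64/125 = 0.512. Their product is 0.2499.
- Minimum follow-up is 12 months and the window is 48 months.
- The significance level is 0.05. Sidedness is not stated; two-sided is assumed.

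**Assumptions (not in the documents)**
- Uniform entry over 36 months, a common cutoff at the end of the window and no dropout. Follow-up is then uniform on 12 to 48 months, with mean 30.
- A constant annual progression risk r of 1%, 2%, 5% or 10%.

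**Formulas**
- Hazard per year: λ = −ln(1 − r).
- Mean event probability over 1 to 4 years: P = 1 − (e^(−λ) − e^(−4λ)) / (3λ).
- Expected events: D = 125 × P.
- Standard error of the log hazard ratio: SE = 1/√(0.2499 × D).
- 95% CI around an observed hazard ratio of 1: exp(±1.96 × SE).

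**Worked case, r = 10%**
- λ = 0.10536, e^(−λ) = 0.9 and e^(−4λ) = 0.6561.
- P = 1 − 0.2439/0.31608 = 0.2284, so D = 28.5.
- SE = 0.374, and the CI is exp(±0.734) = 0.48 to 2.1.

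| Assumed annual risk | Expected progressions | 95% CI if observed HR = 1 | Power for HR 2 |
|---|---|---|---|
| 1% | 3.1 | 0.11–9.3 | 9% |
| 2% | 6.1 | 0.21–4.9 | 14% |
| 5% | 14.9 | 0.36–2.8 | 27% |
| 10% | 28.5 | 0.48–2.1 | 46% |

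**Sensitivity to duration**
- Exactly 12 months each: r = 2% gives 2.5 events and 0.08–11.9; r = 10% gives 12.5 events and 0.33–3.0.
- Full 48 months each: r = 2% gives 9.7 events and 0.28–3.5; r = 10% gives 43.0 events and 0.55–1.8, with 62% power for HR 2.

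**When would a doubling be excluded?** The upper limit falls to 2 when D = (1.96/ln 2)²/0.2499, which is about 32 events. Every row of the table is below that. Of the 12-month and 48-month cases listed, only 10% per year with 48 months for everyone is above it.

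**RFS.** No recurrence rate is given either. As an upper bound on precision, suppose all 125 patients recurred: the CI around an observed HR of 1 would be exp(±1.96/√(0.2499 × 125)) = 0.70 to 1.42.

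**Numbers at risk.** Under the same entry pattern, before events, 24/36 of patients (about 83) can be observed to 24 months and 12/36 (about 42) to 36 months. Estimates at 12 and 24 months are therefore the natural ones to report.

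**The case against.** The strongest reply is that a 12-month minimum is a floor and not the actual follow-up, and that Kaplan-Meier and Cox methods deal with unequal follow-up by censoring. That stands: the minimum is not itself a defect. Under the entry pattern assumed above, the first 12 months make up at most 12/30 = 40% of person-time before events, so it would be wrong to say that PFS is judged mainly on early observation.

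Several stronger readings are tempting and are not supported:

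- *That nobody was followed beyond 48 months.* This is one reading of Study Design. If the window is accrual only, follow-up could be longer. What can be said is that follow-up is not reported.
- *That progression comes later and is rarer than recurrence, so a null PFS result was almost inevitable.* The documents give no rate or timing for either event, and eligibility extends to high- and very high-risk disease. At 10% per year, power for a doubled hazard would be 46%: low, but not negligible.
- *That short duration is the main cause.* The width of the intervals reflects few events in 125 patients at least as much. At 2% per year, giving everyone 48 months only moves the upper limit from 4.9 to 3.5.
- *That PFS should become a supportive outcome.* The results are known, so this would be post hoc outcome switching. It would also leave the RFS claim in place, which rests on the same kind of non-significant result.

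None of this supplies the missing horizon, event counts or intervals.

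**Conclusion.** The point holds as a fault in what the Conclusion claims and in what the Results Summary reports. Demonstrated similarity on RFS and PFS does not follow from non-significance over an unreported follow-up. With follow-up uniform over 12 to 48 months and progression of 1% to 10% per year, about 3 to 29 progressions are expected, and a PFS hazard ratio observed at exactly 1 would not exclude a doubling.

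That result depends on the assumed rates and entry pattern. With roughly 32 or more progressions the interval around 1 would exclude a doubling, so the actual event count decides the matter.

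A reader might infer that follow-up was too short to say anything about progression. The documents do not establish that; they establish only that neither the duration nor the precision is given.

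**What to change.** Keep RFS and PFS as the primary outcomes in Objectives and Outcome Measures. The changes belong in Results Summary and Conclusion.

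1. For each of RFS and PFS, report events per arm, the hazard ratio with its 95% confidence interval, and Kaplan-Meier estimates by arm with numbers at risk at 12 and 24 months. Give median follow-up by arm. This also settles how the 2019 to 2022 window is to be read.
2. Replace the efficacy part of the Conclusion with wording such as: *no difference in RFS or PFS was detected over the observed follow-up*. Add that differences within the reported intervals, in particular for progression, cannot be excluded.

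The estimates come from the Kaplan-Meier and Cox analyses already listed under Statistical Analysis, so no further patients or follow-up are needed. The cost is a narrower claim: the Conclusion would no longer assert that the two substrains have been shown to be similar.
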